## **A. SPECIFIC AIMS**

Populations all over the world are experiencing rapid increases in the prevalence of obesity and diabetes [1-5]. To date, the public health response to the emerging obesity epidemic has been almost totally ineffective. As a first line of response, professional bodies and government organizations have issued prevention guidelines, all of which include recommendations on levels of activity energy expenditure (AEE) [6-10]. However, even if fully implemented, it is not clear that the current recommendations on AEE would impact the trend in age-related weight gain. *In fact, there is virtually no direct evidence that can be brought to bear on the question of whether the obesity epidemic has resulted primarily or even partially from society-wide declines in habitual physical activity (PA).*

To date, epidemiologic research on AEE has relied on very crude measurement tools—primarily questionnaires. These self-reported data capture only a small fraction of the total variance in activity and are potentially confounded when they focus on leisure-time PA. By contrast, direct measurement with doubly labeled water (DLW) provides a precise, unbiased estimate of all forms of non-resting energy expenditure. DLW has also been used to validate the new generation of accelerometers which are efficient measurement tools for larger studies.

In this application we request support to apply these objective measurement tools to examine the “ecology of AEE”. The study will take place in 5 countries, spanning the range of the activity-obesity spectrum, and combine both within-population person-level and between-population ecological analyses. First, we will examine whether an individual’s amount or pattern of AEE is related to adiposity in a diverse sample of 2,500 (i.e., 500 subjects/site x 5 sites). Second, we will test the ecological hypothesis that a decline in levels of AEE is an important cause of the rapid increases in obesity that are currently taking place in many societies. As an exploratory aim we will examine the role of selected adipocytokines and the appetite hormone ghrelin.

*Accordingly, we propose to test the following Hypotheses:*

- 1) AEE is negatively related to percent body fat in the 5 study populations at baseline, independent of dietary intake.
- 2) AEE is negatively related to change in body weight during follow-up, independent of dietary intake.

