## B.1 Physical Activity and Risk of Obesity

The energy budget is defined by the direct relationship between energy intake and expenditure. Obesity can only result from an excess of calories consumed over calories expended. It is often assumed, therefore, that a similarly straightforward, simple relationship exists between variation in AEE within the range of normal for a population and the risk of weight gain. The second conclusion which follows from this line of reasoning is that population-level weight gains taking place have resulted—at least in part—from declining AEE, and small increases in AEE for individuals will prevent weight gain. In fact, neither of these conclusions is justified by theory alone or supported by evidence. Increases in expenditure would normally be accompanied by increases in intake, while excess intake can be stimulated independently by high caloric density of food, changes in food availability, and eating patterns. As pointed out repeatedly by investigators in this field [17-20], the regulation of energy stores and body composition must be seen as a complex, dynamic process influenced by the interplay of factors that modify both intake and expenditure. An individual ultimately uses both biological stimuli, via the hormones that control satiety, and social cues to achieve energy balance [21-24]. Whether variation in patterns of activity observed in modern, free-living populations plays a key role in this process is unknown. Since recommendations to increase AEE to reduce weight gain are at the core of current public health policy this issue deserves careful study.

Large shifts in chronic disease have been associated with recognizable shifts in lifestyle—for example cigarette smoking and lung cancer, and animal fat intake and heart disease [25, 26]. “Macro-level” or ecological relationships are, of course, subject to confounding. However, these relationships must be present for an etiologic hypothesis to be correct, and their absence is a serious weakness for a hypothesis. While lifestyle trends that increase risk of obesity are obviously taking place, it is difficult to identify clear temporal associations. As clearly demonstrated in the trends from the CDC’s Behavioral Risk Factor Surveillance

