## B.2 Activity Energy Expenditure and Risk of Future Weight Gain

Under experimental conditions, increases in activity *with control of energy intake* will obviously lead to weight loss. However, more relevant to population prevention efforts is the question of whether variation in normal activity mitigates the tendency to gain weight. Despite the view that this relationship is self-evident, the data are not convincing. By far, the largest number of studies has employed questionnaires. In most analyses, categories of sedentary activities (e.g., hours of TV watching) or leisure time sports are used as the

exposure measures. In two specialized cohorts, i.e., Nurses and Health Professionals, sub-sets of significant relationships were observed (e.g., TV watching and obesity, increase in vigorous PA and reduction in waist size) [29, 30]. In other prospective surveys, change in PA was an important predictor of weight change, explaining 4.4% of change in body weight in a UK cohort [31] and predicting weight change in both black and white adults over 10 years of follow-up in CARDIA [32]. Occupational activity was predictive of weight change in China [31]. An older review of 16 prospective, observational studies examining the role of PA in the prevention of weight gain among white males found inconsistent results: 3 studies reported an inverse association between baseline PA and weight change, 2 showed a positive association, 4 reported an inverse association between follow-up PA and weight change, and 7 had no association [33]. In addition, other recent large community studies have shown no association [34, 35]. Questionnaires are both insensitive and potentially biased instruments. A RECENT COMPREHENSIVE REVIEW OF VALIDATION STUDIES FOUND THAT ON AVERAGE THE CORRELATION BETWEEN AEE BY QUESTIONNAIRE AND DLW WAS  $\sim 0.2$  (Neilson et al). The challenge in this field is clearly to move toward objective measurement tools.

DLW has been used in 4 observational and longitudinal studies with a minimum follow-up of 12 months in adults (cf. Appendix A, Table 3) [36-39]. Only 3 of these studies—including two of our own—examined weight gain in a population sample [36, 38, 39]. While all three studies found an association between AEE and body composition at baseline, variation in AEE did not predict future weight change. These results are similar

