**Figure 2. Mean BMI in 5 Countries of African Origin, 25-45 year olds**

to our larger pilot data on women in Chicago and Nigeria (cf. Preliminary Studies). Some interventional studies, focusing on the risk of regaining weight after dieting, have suggested that higher AEE is preventive [40, 41]. Accelerometers, either alone or in combination with heart rate monitors, have so far received limited attention in population studies of this question. While several studies have quantified activity, none have yet reported longitudinal results. A varied literature also exists among children using these methods, with similarly equivocal results (cf. Appendix A, Table 4 for summary). To our knowledge, at the present time there are no data using objective measurements that permit the “macro-level” or ecological hypothesis of AEE versus obesity to be tested.

*The question framed in this section is at the heart of our proposal, and therefore we want to*

*be certain it is stated with complete clarity. For sake of emphasis, we repeat the key point. Whether or not variation in AEE by itself influences body fat stores is a fundamental biological and public health question. Under normal circumstances increased activity stimulates increased energy intake which allows the organism to remain in balance. At the present time the “accepted wisdom” states that AEE added to a daily life routine of humans will reduce the risk of obesity. In fact, the available data do not support that “optimistic” view. For example, in a recent well controlled clinical trial involving 468 overweight or obese women, graded increases in exercise led to highly consistent increases in fitness, but did not result in participant weight loss [42]. This result is consistent with the general finding in the literature on this question which shows that increased AEE without intentional calorie restriction does not reduce weight [43-45].*

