## B.9 Summary

Although the “obesity epidemic” has received enormous attention in recent years, the mechanisms through which the energy budget is being perturbed are still not well understood. In particular, the role of declining AEE as a causal mechanism in population-wide increases in relative weight deserves much greater attention. Despite widespread perception that variation in normal activity levels (as opposed to voluntary increases in high-intensity activity, as typical of trials) is correlated with change in weight, the data do not support this conclusion. Research in this vital area has been handicapped by lack of access to precise objective methods of measurement. A new generation of epidemiologic research will be required before we can base causal inferences or public health recommendations on something more than assumptions. As with other chronic CVD, international comparisons could be particularly informative.

The test of our study hypothesis will be “two-sided”. That is to say, the presence or absence of an association can be given a clear interpretation. Of course, given the body of evidence that increased AEE has health advantages, absence of an association would not be taken to suggest that AEE is of no value. Rather, the correct interpretation would be that declining AEE is unlikely to be the driving force behind the rise in obesity, nor will modest increases in AEE be adequate to reverse the trends.

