#### *D.7.1.2 AEE and Weight Change*

The study design contemplates 3 weight determinations over time: one at baseline, a second after 12 months, and a final assessment 2 years after entering the study. To better understand the associations between AEE and body composition, the analysis plan will be carried out in incremental steps corresponding to the degree of sophistication of the statistical methods used.

- 1) Descriptive: Weight change is computed for each subject as the subject's last weight minus baseline weight. The correlation between weight change and AEE will be computed.
- 2) Regression of weight change (as computed above) on AEE will be performed, adjusting for potential confounders of the association.
- 3) AEE will be dichotomized at the median value, resulting in high and low AEE groups. Weight change will be estimated for each individual as the slope of the regression of weight on time (0, 12, and 24 months). Average weight change across AEE groups will be compared. That is, individual regression lines of weight on time will be obtained for each individual, and the average regression among "Low PA" will be compared to the average regression among "High PA" subjects.
- 4) Multilevel analysis (i.e., mixed effect models), which generalizes the previous methods, will be used in our final analysis. This approach will allow for the use of all the available information (i.e., there will be no need to categorize AEE values), thus improving the statistical power [189]. Furthermore, this method allows one to account for the within-subject correlation of the weight determinations and to account (adjust for) subject-specific covariates that may confound the associations. In addition, the dependence of weight change on AEE values can be specifically modeled by the use of random coefficients. Specifically,

$$\text{Level 1: } W_{ij} = \beta_{0i} + \beta_{1i} T_{ij} + \varepsilon_{ij}$$

$$\text{Level 2: } \beta_{0i} = \gamma_0 + \gamma_1 AEE_i + \Omega X_i + \xi_{0i}$$

$$\beta_{1i} = \alpha_0 + \alpha_1 AEE_i + \Psi Z_i + \xi_{1i}$$

$$\varepsilon_{ij} \approx N(0, \sigma^2); \xi_{0i} \approx N(0, \delta_0^2); \xi_{1i} \approx N(0, \delta_1^2); \text{corr}(\xi_{0i}, \xi_{1i}) = \delta_{01}$$

$$\text{corr}(\varepsilon_{ij}, \xi_{0i}) = \text{corr}(\varepsilon_{ij}, \xi_{1i}) = 0$$

$$i = 1, \dots, n; \quad j = 0, 1, 3$$

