Where  $T_{i1} = 0$ ,  $T_{i2}=12$ , and  $T_{i3}=24$  correspond to the three times at which weight will be measured for the  $i$ -th subject;  $X_i$ , and  $Z_i$  are potential confounders; and  $\Omega$  and  $\Psi$  are model parameters associated to the confounders. Confounders will include demographic variables and EI variables (e.g. total intake, percent calories from fat, etc). This approach corresponds to a multivariate nutrient density method suggested in the literature [73]. The effect of type of food most frequently consumed (e.g. vegetables, industrially processed foods, etc) will be accounted for by including dummy variables in our multivariate regression models. Note that the parameter  $\beta_{1i}$ , in the Level-1 equation, represents the weight change of the  $i$ -th subject. Thus, the Level-2 equation for this parameter models the dependence of weight change on AEE after adjusting for other covariates. A similar interpretation for the intercept parameter,  $\beta_{0i}$ , holds. In both instances site-specific factors could be included.

The multilevel approach can be extended to accommodate time-varying covariates, which we will apply to investigate the effect of changing AEE on weight change. In addition, the effect of AEE in the  $i$ -th subject ( $\Delta AEE_i$ ) on weight change will be assessed by replacing  $AEE_i$  in the Level 2 step of the multi-level analysis above by ( $\Delta AEE_i$ ).

Finally, one additional co-variate capturing exposure information will be created which will define the pattern of AEE. After examining the within-person distribution over the monitored days (eg, within-person SD) we will use both continuous and categorical transformations to characterize "consistent vs variable" patterns. Our pilot data suggest substantially more consistent patterns in Nigeria vs. the US and this may impact on the AEE-weight relationship.

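### The final weight-change model adjusts for total energy intake, which the protocol says responds to activity, and no matching model without intake is specified

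*Combined protocol and SAP*

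**What the plan says.** Section D.7.1.2 plans the weight-change analysis in four steps. Step 1 is an unadjusted correlation, labelled descriptive. Step 2 is a regression adjusted for confounders that are not listed at that point. Step 3 splits AEE at the median and compares individual weight slopes, naming no covariates. Step 4, a multilevel model with AEE kept continuous, "will be used in our final analysis". For that model, "Confounders will include demographic variables and EI variables", with the examples "e.g. total intake, percent calories from fat, etc".

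Hypothesis 2 (Section A, repeated in D.7.1) is that "AEE is negatively related to change in body weight during follow-up, independent of dietary intake".

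On how intake behaves, Section B.1 says: "Increases in expenditure would normally be accompanied by increases in intake". The emphasised text of Section B.2 says: "Under normal circumstances increased activity stimulates increased energy intake which allows the organism to remain in balance". Section B.2 also treats weight loss as self-evident when activity rises and intake is controlled, and says that "more relevant to population prevention efforts is the question of whether variation in normal activity mitigates the tendency to gain weight". If no association is found, Section B.9 would conclude that falling AEE is not the main cause of rising obesity, "nor will modest increases in AEE be adequate to reverse the trends".

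**The concern.** A variable that responds to the exposure and passes on part of its effect is a mediator. Holding it fixed removes the part of the effect that runs through it. Here that part is the compensation which, on the protocol's own account, may cancel the effect of activity on weight. The adjusted slope then estimates the effect of AEE at fixed intake, the case Section B.2 sets aside as self-evident.

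The wider aims need the effect with intake free to respond: the conclusion in Section B.9, the minimum activity for preventing weight gain in Section B.4, and the AEE threshold in Section E.4. If compensation were complete, the final model could still give a significant negative slope. The study could then miss the null conclusion that Section B.9 describes, or the slope could be taken as evidence that ordinary activity prevents weight gain. The plan neither discusses intake as a mediator nor says how to read adjusted and unadjusted results that differ.

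**Working it through.** The plan gives no figure for this point, so there is none to reproduce. The multilevel model is reduced here to a regression of annual weight change on AEE, with and without recorded intake; the AEE term in its slope equation plays the same part.

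**Model.** Let EI be intake, REE resting expenditure, c the fraction of AEE matched by intake, and e intake unrelated to AEE and REE. Let m be recall error and k the kg/y per kcal/d of imbalance. REE, e and m are taken as uncorrelated with AEE and with each other.

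- EI = REE + c·AEE + e
- Weight change = k(EI − REE − AEE) + noise = k(c − 1)·AEE + k·e + noise
- Recorded intake EI* = EI + m

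**AEE slope.**

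- Without EI*: k(c − 1)
- With EI*: k(c − 1) − c·k·L, where L = var(e) / [var(REE) + var(e) + var(m)]

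L is the share of recorded-intake variance, at given AEE, that is due to intake unrelated to AEE and REE. At full compensation (c = 1) the slopes are 0 and −kL.

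**Inputs.**

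- k: Section B.6 equates 1.5–2.0 lb/y with about 30 kcal/d. That is 0.680/30 = 0.023 to 0.907/30 = 0.030.
- SD(REE): 157 and 212 in Table 3, average about 185 kcal/d.
- SD(AEE): 311 and 299 in Table 3, taken as 300 kcal/d.
- SD(e), the between-person imbalance when c = 1: not given. Section D.8 gives only a net level of 20–40 kcal/d. Assumed 30, 100 or 200.
- SD(m) for two 24-hour recalls: not given. Assumed 300, 500 or 800 kcal/d.

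**Size at c = 1, SD(m) = 500.**

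- SD(e) = 30: L = 900/(34,225 + 900 + 250,000) = 900/285,125 = 0.0032. Slope per 100 kcal/d: −0.007 to −0.010 kg/y.
- SD(e) = 100: L = 10,000/(34,225 + 10,000 + 250,000) = 10,000/294,225 = 0.034. Slope per 100 kcal/d: −0.08 to −0.10 kg/y.

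Per AEE SD of 300 kcal/d, the second case is −0.23 to −0.31 kg/y, or 30% to 42% of the mean gains of 0.76 and 0.73 kg/y in Section C.2.2.2. The first is −0.02 to −0.03 kg/y, about 3% to 4%.

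**Incomplete compensation.** With c = 0.9, SD(e) = 100 and SD(m) = 500, the slope is −0.100k without intake and −0.131k with it. With c = 0.5 it is −0.500k and −0.517k. The adjustment matters most near full compensation.

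**Chance of a significant negative slope at c = 1.** This takes N = 2,000 (Section D.7.1.1.1), a one-sided 5% test (assumed for Hypothesis 2) and weight noise equal to the imbalance term (assumed). The second figure in each cell uses accelerometer reliability 0.38, the square of the 0.62 correlation in Section B.5.

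| SD(e) | SD(m) 300 | SD(m) 500 | SD(m) 800 |
|---|---|---|---|
| 30 | 54% / 22% | 22% / 12% | 11% / 8% |
| 100 | 100% / 89% | 88% / 48% | 37% / 19% |
| 200 | 100% / 100% | 100% / 92% | 81% / 44% |

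Without intake in the model the rate is about 5% throughout (simulated 4.3% to 5.6%).

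**The case against.** The adjustment is deliberate and fits the hypothesis. Hypothesis 2 asks for a diet-independent association, and Section B.6 argues that expenditure has its own influence on energy stores. For that target the model is valid. Intake is also more than a mediator: Section B.1 says food density, availability and eating patterns can raise it independently of activity, and Section D.7.1.3 names it as a potential confounder. A slope without intake is therefore not free of bias. All of this stands, and it is why the adjusted test should be kept.

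A reader might infer that every planned weight-change analysis conditions on intake. The documents do not support that: steps 1 and 3 name no such adjustment, and the sample-size argument in Section D.7.2 uses step 3. But step 1 is only descriptive and step 3 dichotomises AEE. Neither gives a continuous slope adjusted for demographics but not intake.

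A reader might also infer that the investigators will claim prevention from the adjusted slope, or that a false protective result is bound to appear. The plan does not say the first. The conclusion it spells out is for an absent association, which a negative artefact would work against. The second does not follow either: poor recall and small between-person imbalance shrink the artefact almost to nothing.

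**Conclusion.** The concern holds as a gap in what the final analysis can support, not as an error in the test of Hypothesis 2. The final model calls total intake a confounder, while the background describes it as a response to activity. Its slope is the effect at fixed intake and cannot alone answer the question in Section B.2 or support the conclusion in Section B.9.

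The direction of the artefact follows from the algebra whenever intake varies for reasons other than AEE and resting expenditure. Its size cannot be fixed from the documents, because the SDs of imbalance and recall error are not given. Over the assumed ranges, the chance of a significant negative slope under full compensation runs from 8% to 100% at N = 2,000, against a nominal 5%. The kg/y figures also assume that the energy conversion in Section B.6 applies between persons and, unlike the second figures in the table, that AEE is measured without error.

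**What to change.** In Section D.7.1.2, keep the intake-adjusted multilevel model as the test of Hypothesis 2. Pre-specify the same model without total intake, with demographics and diet composition retained, and report the two AEE slopes side by side. Describe the first as the effect at fixed intake and the second as the effect with intake free to respond. State in advance that no claim that AEE prevents weight gain will rest on the intake-adjusted slope alone, and how a disagreement between the slopes will be read.

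This needs one more model and no new data. Its downside is that the slope without total intake carries any confounding by intake habits unrelated to activity, so it should not automatically override the adjusted one. The text should say so.

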Following transformation of the appropriate exposure and outcome variables, Fisher's Z-transformation test will be applied in order to test hypotheses involving correlations. The resulting parametric test will be more powerful than other distribution-free approaches. The results will be corroborated by applying Spearman rank correlations and another parametric test based on the concordance coefficient introduced by Lin [182] and later extended by Chinchilli and colleagues to include repeated measures [183]. Lin's concordance correlation allows the comparison of the correlations accounting for possible differences in the mean values of the two variables under consideration. Furthermore, approximate permutation tests [184, 185] will be implemented using each of the three statistics: Pearson, Spearman and Lin's concordance, to compare agreement of the association between AEE and BMI across the three groups under investigation.

Correlation coefficients will be estimated using the Pearson correlation and confidence intervals constructed after applying the Fisher's Z-transformation. Furthermore, computer intensive statistical methods, such as bootstrapping, will be used to construct confidence intervals for both parametric and nonparametric approaches. Comparisons of these correlations will be carried out using this statistic for 1 and 2 samples [186], as well as approximate permutation tests [184, 185]. In addition, multivariate regression analysis will be fit to adjust for potential confounders. Confounders will include age, gender, and any other significant

predictors defined by the univariate analyses. Potential non-linear functions will be explored to see if they fit the data better. Sub-group analyses will be undertaken, with participants in each site divided by gender.

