#### *D.7.1.1.2 AEE, Adipocytokines and Diabetes*

We will have measures of fasting glucose and insulin, adiponectin, ghrelin and leptin on this unique sample of 5 populations of African origin. The following additional variables will be collected: age, gender, place of birth, prior medical history, occupation, education, height, weight, activity by questionnaire, pregnancy history, and season of exam.

In the analysis phase we will first compare the descriptive characteristics in each population (e.g., mean adipocytokine/hormone values and prevalence of hyperglycemia). We will explore the univariate correlation structure for the continuous variables listed above. We will then construct multivariable regression models to assess the potential independent role of AEE as a predictor of risk factor status independent of body composition. Risk factor status will be examined as continuous and categorical outcomes. For instance, how is insulin level affected by AEE after accounting for body composition?

An important focus of these analyses will be looking for potential heterogeneity of risk relationships across sites. Three main aspects are of interest, namely whether the AEE-risk factor (e.g. insulin level) relationship is present, or of the same magnitude, in each sample and whether there exists co-variation with the mean level of AEE; testing for interaction will be undertaken where appropriate. Precisely,

*Relative effect of AEE on risk factor:* We will examine the magnitude of the association using 1) regression coefficients; 2) standardized regression coefficients. This approach allows within and between site comparisons. It is recognized that cross-site comparisons could be problematic when using standardized regression coefficients since the standard deviation of the variables involved may differ across sites. In this case, standardized regression coefficients will be obtained using pooled estimates of the mean and standard deviation.

*Co-variation of the association with mean level of AEE:* Multilevel models will be applied, in which the site specific variable, mean AEE, will be used to estimate the effect of the average AEE on the regression coefficient.

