*Interactions between AEE and site:* Multiplicative interaction terms will be included in regression models to assess how much site modifies the association between AEE and the risk factor. We are fully aware of the lack of statistical power to test this type of hypotheses and thus results will be exploratory in nature. Thus, one might anticipate that anthropometric and AEE measures are stronger in low risk population samples than in the US. In addition, we will test whether the slope of the exposure-outcome relationships are influenced by the mean BMI of the population using multilevel regression models.

Questionnaire data on AEE will be summarized using methods previously developed [188]. Mean activity levels and prevalence of inactivity will be assessed in relation to objective measures of EE and the relevant outcome variables. As a sub-analysis we will describe types of activities reported to assess overall population patterns.

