Although the study is not powered to test for differences in the association across sites (i.e., effect modification), we will undertake this task to ensure that large differences among the correlation coefficients do not exist. In addition, sites in which the correlation coefficient is deemed to be similar will be combined, and then comparisons of the correlations will be performed. For the sake of illustration, assume that 2 sites ( $n = 150$  individuals) are compared to other 2 sites ( $n = 150$  individuals). Thus, a two-sample, one-sided test of the correlations, assuming -0.4 versus -0.65, will yield over 91% power, whereas the power will be over 80% for comparison of -0.45 and -0.65, and between -0.35 and -0.6 the power is greater than 85%. Combining the data samples from all 5 sites and assuming constant

association will demonstrate a correlation between AEE and change in body composition of -0.15 or smaller (larger in absolute value) with over 83% power.

3) Mean levels of AEE are negatively related to mean levels of obesity/relative weight among the populations.

As previously demonstrated, sample sizes within sites will allow us to rule out correlations larger than 0.33 (absolute value), even when AEE is determined by DLW. Furthermore, we have estimated (cf. Preliminary Studies) that the within-site correlation between AEE and body composition of individual data could be as large as 0.6. We anticipate that the correlation between mean AEE levels and mean body composition will exceed 0.85. This estimate is justified in the following manner. A Fisher's Z-transformation 5%-significance test will have over 55% power to detect this correlation with 5 values corresponding to the 5 sites of the study. However, after dividing our samples by gender there will be 10 observations (2 X 5 countries), resulting in over 95% statistical power. Assuming an effective sample size of 7, to account for within-country correlations, the statistical power is 80%. Note that additional power will be gained when weighted linear regression methods are applied to estimate the correlation (slope) between AEE and body composition using meta-regression. Given the strong a prior hypothesis we can also compare mean AEE in the groups with the highest and lowest rates of obesity to test the ecological association.

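### Site terms are optional in the final weight-change model and unnamed in the baseline adiposity model, so a pooled person-level AEE estimate would mix within-site and between-site associations

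*Combined protocol and SAP*

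**What the plan says.** Section A sets out a design that will "combine both within-population person-level and between-population ecological analyses". Hypothesis 1 (AEE and percent body fat at baseline) and Hypothesis 2 (AEE and weight change) belong to the person level. Hypothesis 3 (site mean AEE and site mean obesity) belongs to the ecological level.

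- **Hypothesis 2.** The Level 1 and Level 2 equations in D.7.1.2 contain time, AEE and confounder vectors X and Z. The commitments are "Confounders will include demographic variables and EI variables (e.g. total intake, percent calories from fat, etc") and, for diet pattern, "The effect of type of food most frequently consumed (e.g. vegetables, industrially processed foods, etc) will be accounted for by including dummy variables". On site the text says only "In both instances site-specific factors could be included".
- **Hypothesis 1.** D.7.1.1.1 states "Confounders will include age, gender, and any other significant" predictors found by univariate analysis. Site is not on the list, although subgroup analyses by site and gender are planned.
- **Pooling.** The DLW calculation in D.7.2, item 2b, is introduced by "Combining the data samples from all 5 sites and assuming constant" association. Sites are combined when their correlations look alike; nothing is required of their means.
- **Contrast.** For the risk-factor outcomes in D.7.1.1.2 the plan does name site: "Multilevel models will be applied, in which the site specific variable, mean AEE, will be used to estimate" how mean AEE affects the coefficient, and "Multiplicative interaction terms will be included in regression models to assess how much site modifies the association between AEE and the risk factor".

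**The concern.** When people from several sites are pooled without site terms, the AEE coefficient is a weighted average of the within-site slope and the slope across site means. D.3.2 says the sites were chosen because their BMI differs, and Table 1 shows that mean AEE differs too, so the between-site part need not be small. Similar within-site correlations, the plan's condition for pooling, do not remove it.

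B.7 treats agreement between the individual and group levels as grounds for inference. D.7.2 relies on testing individual-level relations first as the guard against ecological confounding. Per-site estimates can provide that guard. A pooled estimate without site terms cannot, because it already contains part of the Hypothesis 3 contrast. Leaving site optional also lets the choice be made after the data have been seen.

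**Working it through.** **1. The plan's own power figure.** D.7.2 gives over 83% power for a pooled correlation of -0.15. By Fisher's z, power = Φ(atanh(0.15)·√(n−3) − z), with atanh(0.15) = 0.1511.
- n = 375 (5 × 75), two-sided 5%: Φ(0.1511 × √372 − 1.960) = 83.0%.
- n = 300 (after the 20% attrition in D.1.1), one-sided 5%: Φ(0.1511 × √297 − 1.645) = 83.1%.

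The figure reproduces under either reading. It treats the pooled people as one sample.

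**2. Formula for pooling.** For k equally weighted sites with within-site correlation rw:

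r = [mean(rw·sx·sy) + cov(site means)] / √{[mean(sx²) + var(site means of x)] × [mean(sy²) + var(site means of y)]}

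**3. Baseline, with rw = 0.** Any non-zero result then comes from site differences alone.

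*Table 3* (Nigerian and US women, n = 150 and 180, percent fat 29.3 and 39.8 with SD 8.6 and 9.0). For AEE/kg (13.5 and 10.0, SD 6.0 and 3.8), the covariance of the means is 3.5 × (−10.5)/4 = −9.19. The variance terms are 25.22 + 3.06 = 28.28 and 77.48 + 27.56 = 105.04. So r = −9.19/√(28.28 × 105.04) = −0.169.

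*Table 1* (five sites, 16 to 23 people per sex and site, BMI standing in for percent fat). For women in kcal/d, r = 498.3/√[(163,270 + 38,718) × (50.33 + 7.31)] = +0.146.

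The 95% ranges below come from redrawing each site mean as normal(mean, SD/√n), 20,000 draws, using sample BMI for Table 1.

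| Source | AEE scale | Pooled r | 95% range |
|---|---|---|---|
| Table 3, women | AEE/kg | −0.17 | −0.22 to −0.11 |
| Table 3, women | adjusted AEE | −0.04 | −0.09 to +0.02 |
| Table 3, women | PAL | −0.02 | −0.08 to +0.04 |
| Table 1, women | kcal/d | +0.15 | +0.05 to +0.24 |
| Table 1, women | AEE/kg | +0.10 | +0.01 to +0.19 |
| Table 1, women | adjusted AEE | +0.11 | +0.02 to +0.20 |
| Table 1, women | counts | +0.10 | 0.00 to +0.19 |
| Table 1, men | kcal/d | +0.11 | −0.02 to +0.23 |
| Table 1, men | AEE/kg | −0.03 | −0.14 to +0.09 |
| Table 1, men | adjusted AEE | 0.00 | −0.12 to +0.12 |
| Table 1, men | counts | −0.04 | −0.15 to +0.08 |

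With Table 1's population BMI in place of sample BMI, women run from +0.05 to +0.09 and men from −0.01 to +0.08.

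**4. Baseline, with the correlations the plan expects.** D.7.2 expects −0.5 to −0.6. The pooled value would be −0.27 to −0.54 (Table 1) or −0.45 to −0.64 (Table 3). The size changes but the direction does not.

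**5. Weight change, with rw = −0.15.** The documents do not give the SD of annual gain, so it is assumed.
- *C.2.2.2 gains* (0.73 and 0.76 kg/y, Nigerian and US women), Table 3 AEE, SD 1 to 4 kg/y: −0.14 on AEE/kg, and −0.15 on adjusted AEE and PAL.
- *B.3 rates* (0.4 kg/y Nigeria, 1.4 kg/y Jamaica), Table 1 AEE for those two sites, SD 2 to 4 kg/y: in kcal/d, +0.01 to −0.06 for men and −0.02 to −0.08 for women. On AEE/kg, 0.00 to −0.06 for men and −0.08 to −0.11 for women. For example, men in kcal/d at SD 2: (−83.85 + 90.5)/√[(78,822.5 + 32,761) × (4 + 0.25)] = +0.01.

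**The case against.** The person-level design is largely within-site. Descriptive tables are by gender within site, Hypothesis 1 is sized at 75 per site, and Hypothesis 2 is sized against 500 per site. D.7.1.3 tests whether the activity–BMI slope differs between pairs of sites, and such a test would normally carry site main effects. The five-site statement in D.7.2 is a power calculation, not a specified estimator. D.7.1.2 does not define n, so the model could be fitted site by site. Birth place, food-type dummies or univariate screening might bring site in. Differences in baseline weight enter the model's intercept, so the weight-change slope is distorted only if site rates of gain vary with site AEE. The pilot cells are small, BMI replaces percent fat, nothing is adjusted, and the protocol itself warns against reading its pilot subgroups.

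Much of this stands as a limit on scope and size. The per-site analyses are valid, and the effect on weight change may be negligible. It does not close the gap. The slope test is a heterogeneity check on BMI and does not put site into the AEE estimate for either hypothesis. The possible stand-ins are not commitments to site. If site-specific factors means site-level factors, as in D.7.1.1.2, they would be constant within one site, so the permissive sentence points to a multi-site fit. That wording is not wholly unambiguous, since D.4.4 also applies site-specific to foods.

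**Conclusion.** The concern holds for pooled estimates under Hypotheses 1 and 2, and only for those. The omission is clear from the text; its size is not settled. At baseline, site differences alone could give a pooled correlation of about −0.17 to +0.15. Women in Table 1 lie just above zero, and the sign for men is not established. If the within-site relation is as strong as the plan expects, the direction survives and only the size is affected. For weight change, the result depends on which of the protocol's own rates are used: essentially no distortion with the Nigeria–US pair, and most of a −0.15 correlation hidden in some Nigeria–Jamaica cases. All figures assume equal site weights and no covariate adjustment, whereas the planned models adjust for age, gender and diet. They show possible direction and size and do not forecast bias. The point is worth correcting because the two-level argument needs a person-level estimate free of the between-country contrast.

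**What to change.** In D.7.1.2, replace the optional sentence with a commitment to fixed site indicators in both Level 2 equations (intercept and slope). In D.7.1.1.1, add site indicators to any pooled regression, and do not rely on birth place or food-type dummies as substitutes. Report the site-adjusted AEE coefficient as the person-level result. Obtain the pooled DLW correlation by combining site-specific Fisher z values weighted by n − 3. Site-centred AEE with the site mean as a separate term would also separate the levels; whichever form is chosen should be fixed in advance.

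No new data are needed. The power cost for a correlation of −0.15 uses the formula in the working, with n − 3, n − 7 (four indicators) or n − 15 (five z values) under the root:

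| Case | No site terms | Four indicators | Combined z |
|---|---|---|---|
| n = 375, two-sided | 83.0% | 82.6% | 81.8% |
| n = 300, one-sided | 83.1% | 82.7% | 81.8% |
| n = 300, two-sided | 74.0% | 73.5% | 72.3% |

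The loss is at most 1.8 points. This holds the within-site correlation at −0.15 and covers the DLW correlation; the cost for the accelerometer mixed model was not computed.
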